10.3 Reporting Requirements

For this study, all Master Adverse Events Documents collected on patients for this protocol will be reviewed by the Principal Investigator on a monthly basis to determine if a serious safety problem has emerged that result in a change or early termination of a protocol such as:

- dose modification,
- suspending enrollment due to safety or efficacy, or
- termination of the study due to a significant change in risks or benefits.

Treatment options in this study are standard of care per NCCN guidelines. Therefore there are no specific end points.

As per the CTSC DSMP, any protocol modifications, problematic safety reports, unanticipated problems, and suspension or early termination of a trial must be reported to all members of the research team. Suspension and early termination of a trial must also be reported immediately to the Director of Quality Assurance (DQA) who will promptly notify the sponsor and the UTHSCSA IRB.

The PI will review the Master Adverse Events documents to determine the significance of the reported events and will file the Investigator Initiated Study Quarterly DSMC Report Form on a quarterly basis with the CTSC DSMC. The Investigator Initiated Study Quarterly DSMC Report Form includes information on adverse events, current dose levels, number of patients enrolled, significant toxicities per the protocol, patient status (morbidity and mortality), dose adjustments with observed response, and any interim findings. Any trend consisting of three or more occurrences of the same event will be reported to the CTSC DSMP for independent review outside of the quarterly reporting cycle, which begins three months following

protocol start up. Conflict of interest is avoided by the independent review of the CTRC DSMC and by ongoing independent review of adverse events trends by the Director of Quality Assurance.

All SAE and UPRISO's will be reported following CTRC and UTHSCSA institutional guidelines.

UTHSCSA SAE/UPRISO REPORTING REQUIREMENTS		
Type Event	Report to	Timeframe
All AE, SAE and UPIRSO	Regulatory Affairs and DQA	Same as other notification timeframes except for SAE/AE which should be reported on Monday for the prior week
SAE	Clinical Trial Sponsor	within 24 hours
AE/SAE	UTHSCSA IRB	Annually
UPIRSO - all	Clinical Trial Sponsor	within 24 hours of the PI determining a UPIRSO exists
UPIRSO - life threatening	UTHSCSA IRB	within 48 hours of the PI determining a UPIRSO exists
UPIRSO - non-life threatening	UTHSCSA IRB	within 7 days of the PI determining a UPIRSO exists

AE's and SAE events that occur during clinical trials with or without an Investigational New Drug (IND) application are mandatory reports submitted to FDA via Medwatch FDA F3500A *within 15 days for events that have at least a possible relationship with the drug.*

10.4 Assuring Compliance with Protocol and Data Accuracy

As with all studies conducted at CTRC, the PI has ultimate responsibility for ensuring protocol compliance, data accuracy/integrity and responding to recommendations that emanate from monitoring activities. Source verification of data will be performed every twelve week. Protocol compliance, data accuracy and reporting of events is further ensured by an annual audit conducted by the Data Safety Officer, whose audit report is shared with the PI, the research team, and will be reviewed by the CTRC DSMC.

11. STATISTICAL CONSIDERATIONS:

For this pilot non-inferiority study, we aim to randomize **30** evaluable patients (**radical cystectomy: n=15, chemoradiation: n=15**).

Categorical outcomes will be summarized with frequencies and percentages. Continuously distributed outcomes will be summarized with the sample size, mean, standard deviation, median, minimum and maximum. A consort diagram giving the number patients screened, the number of screen failures, the number randomized, the number lost to follow-up by reason, and the number completing the study by treatment arm will be created. In Aim 1a we will test the hypothesis that chemoradiation therapy is non-inferior to radical cystectomy with regard to change in quality of life at 36 months relative to baseline. In Aim 1b, we will test the hypothesis that chemoradiation is non-inferior to radical cystectomy with regard progression free survival and bladder intact survival. With regard to Aim 1a, assuming the 50% (p_2) of patients randomized to radical cystectomy and 60% (p_1) of patients randomized to chemoradiation will experience improvement in quality of life at 3 years relative to baseline and a 5% margin (Δ) of non-inferiority, this study would require $n=171$ subjects per group to attain 80% power for testing $H_0: p_1 - p_2 \leq \Delta$ versus $H_1: p_1 - p_2 > \Delta$ with $\alpha=5\%$. The non-inferiority of chemoradiation compared with radical cystectomy with regard to changes in quality of life (Aim 1a) will be assessed with Fisher's exact test. Progression free and bladder-intact survival (Aim 1b) will be summarized by treatment arm with Kaplan-Meier curves and supporting tabulations and non-inferiority will be assessed with a logrank test. The significance of treatment arm differences with regard to biomarkers (Aim 2a) will be assessed with t-tests or Wilcoxon tests. Pairwise correlations between biomarkers will be displayed overall and by treatment arm. Logistic regression will be used to find a best linear predictor of treatment arm in terms of multiple biomarkers. Biomarkers may be log transformed prior to analysis. Feasibility (Aim 2b) will be assessed with a new power and sample size calculation. If the logistic regression model fails in Aim 2a, random forests will be attempted. If the logrank test fails in Aim 1b, Fisher's exact test will be used. R (v3+, Vienna, Austria) or SAS (SAS Institute, Cary, North Carolina) software will be used throughout.

REFERENCES

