3.3 Randomization Procedure

A total of 30 patients will be randomized to either chemoradiation group (n=15) or radical cystectomy (with or without neoadjuvant chemotherapy group, n=15). Permuted block randomization process through sequentially numbered, opaque sealed envelopes will be utilized in assigning participants into either radical cystectomy or chemoradiation group. All subjects will be randomized in blocks of size 2. A randomization list containing sequence numbers and treatment assignments will be prepared by the statistician and used as the sole basis for treatment assignments throughout the study.

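### Section 11 keeps confirmatory non-inferiority tests, and prints only a 171-per-group power calculation, for a pilot of 15 per arm that has about 13% power on its own Aim 1a inputs

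*Combined protocol and SAP*

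**What the plan says.** The size is fixed in two places. Section 3.3 states: "A total of 30 patients will be randomized to either chemoradiation group (n=15) or radical cystectomy" (the cystectomy arm is also 15). Section 11 repeats that size in the sentence that begins "For this pilot non-inferiority study, we aim to randomize": 15 per arm, 30 evaluable in all.

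Section 11 then commits to formal tests. For quality of life at 36 months: "In Aim 1a we will test the hypothesis that chemoradiation therapy is non-inferior to radical cystectomy". A parallel sentence covers progression-free survival and bladder-intact survival (Aim 1b). Fisher's exact test is named for Aim 1a and the logrank test for Aim 1b, each as the means of assessing non-inferiority.

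The only power statement concerns Aim 1a: "this study would require $n=171$ subjects per group to attain 80% power". Its inputs are 3-year improvement rates of 50% after cystectomy and 60% after chemoradiation, plus "a 5% margin (Δ) of non-inferiority", with alpha of 5% and sidedness not stated.

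Section 11 gives no power or precision for 15 per arm, no confidence interval for any arm difference, and no margin or event count for Aim 1b. It does not call the tests exploratory. Section 1 and Aim 2b in Section 2.2 do describe the study as a pilot that will inform a larger, adequately powered trial.

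**The concern.** The plan's stated purpose and its analysis section do not match. The purpose is feasibility; the analysis is three non-inferiority tests. The sole power figure belongs to a trial more than eleven times as large (171/15 = 11.4), yet the sentence that gives it refers to this study.

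Two things are at stake. First, a reader cannot learn from Section 11 how little 30 patients can say about non-inferiority. Second, Fisher's and logrank tests as named are tests of no difference and do not use the margin. At this size they will usually be non-significant. If such a result were reported as non-inferiority, the claim would have almost no evidential content, in a comparison of bladder preservation with bladder removal for muscle-invasive cancer.

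**Working it through.** **Inputs (Section 11 unless noted).** p1 = 0.60 (chemoradiation), p2 = 0.50 (cystectomy), margin 5 points, 80% power, alpha 5%; 15 per arm (also Section 3.3). The margin is taken as −5 points on p1 − p2, because that is the reading under which 171 reproduces. The hypotheses as printed carry no minus sign; read literally as +5 points, the formula would give 1,539 per group.

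**Step 1: reproduce the plan's figure.**
n per group = [p1(1−p1) + p2(1−p2)] × (z_alpha + z_power)² / (p1 − p2 + margin)²
- Variance term: 0.24 + 0.25 = 0.49. Distance: 0.10 + 0.05 = 0.15.
- One-sided 2.5%: 0.49 × (1.960 + 0.842)² / 0.15² = 170.93 with unrounded z values, so 171. This matches.
- One-sided 5%: 134.64, so 135. This does not match.

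The plan's 171 therefore corresponds to one-sided 2.5%.

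**Step 2: power at 15 per arm.**
- Standard error = √(0.49/15) = 0.1807.
- One-sided 2.5%: Φ(0.15/0.1807 − 1.960) = Φ(−1.130) = 12.9%.
- One-sided 5%: Φ(0.15/0.1807 − 1.645) = Φ(−0.815) = 20.8%.
- Exact enumeration of all 16 × 16 outcomes: at one-sided 2.5%, 13.4% (Farrington–Manning) and 13.8% (Wald); at one-sided 5%, about 23% for both.

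The plan gives no dropout rate. If 12 per arm were evaluable (an assumption), power at one-sided 2.5% would be about 11%.

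**Step 3: precision at 15 per arm.**
- 95% half-width = 1.960 × 0.1807 = 35.4 points, about seven times the margin (35.4/5 = 7.1).
- An observed 10-point advantage would give roughly −25 to +45 points.
- At 171 per group the half-width would be about 10.5 points.

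**Step 4: Fisher's test at 15 per arm (exact enumeration, two-sided 5%).**

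| True rates, chemoradiation v cystectomy | Non-significant |
|---|---|
| 60% v 50% | 96.7% |
| 30% v 50% | 90.3% |
| 20% v 50% | 75.4% |

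If the test is instead read as rejecting no difference in favour of chemoradiation, it does so at 60% v 50% in about 3% of trials at one-sided 2.5%, or 7% at one-sided 5%.

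**Step 5: Aim 1b.** The plan gives nothing to reproduce, so this is only a bound. With D events, equal arms and a true hazard ratio of 1, the margin that gives 80% power at one-sided 2.5% is exp[(1.960 + 0.842)/√(D/4)].
- D = 30 (every patient has an event, the upper limit): exp(2.802/2.739) = 2.8.
- D = 15 (an assumption): exp(2.802/1.936) = 4.2.

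**The case against.** The strongest reply is that the gap is in effect disclosed. The protocol calls itself a pilot, Sections 1 and 2.2 point to a separate powered trial, the 171 is worded conditionally, and feasibility is to be judged by a fresh sample size calculation. Nowhere does the plan claim 80% power for 30 patients. All of this stands. A reader might infer that 15 per arm is itself a mistake, or that the study must grow to 171 per group; the documents do not support that. What the reply leaves unanswered is that Section 11 still states the tests as confirmatory and ties 171 to this study.

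A reader might also infer that the plan will declare non-inferiority from a non-significant p-value. It does not say so. Section 11 writes its hypotheses so that non-inferiority requires rejecting the null. If Fisher's test were used that way, a false claim at 30% v 50% would be very rare (about 0.02% of trials at one-sided 2.5%, 0.08% at 5%). The percentages in Step 4's table are a risk only under the other reading, which the text leaves open. The failure to use a margin would also persist at 171 per group; it is a separate weakness that the small size makes more consequential.

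Finally, low power does not invalidate a test. A margin-based test at 15 per arm could succeed: with 7/15 improving after cystectomy, 12/15 after chemoradiation would suffice (Farrington–Manning, one-sided 2.5%). It would be wrong to say that non-inferiority cannot be shown.

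**Conclusion.** The point holds as a mismatch within the plan between a feasibility pilot and a confirmatory analysis section. For Aim 1a, a margin-based test at 15 per arm has about 13% power at one-sided 2.5%, or 21% at one-sided 5%, against the 80% printed for 171 per group. A non-inferiority conclusion is therefore very unlikely to be supported, and the tests named would not be the ones to support it.

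These figures rest on the plan's own rates of 60% and 50%, a margin of −5 points and no loss of evaluable patients. They apply to Aim 1a only. For progression-free and bladder-intact survival the shortfall is inferred, because the plan gives no margin, event count or power. The risk of a mistaken claim from a non-significant Fisher result depends on an interpretation that the plan neither states nor rules out.

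**What to change.** Amend Section 11, with no extra patients:

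1. State that the pilot is not powered for non-inferiority (about 13% for Aim 1a at one-sided 2.5%), that the arm comparisons are exploratory, and that no non-inferiority conclusion will be drawn.
2. Replace the Fisher and logrank non-inferiority assessments with arm differences and two-sided 95% confidence intervals: a difference in proportions for Aim 1a, and a hazard ratio or Kaplan–Meier difference for Aim 1b. Section 9.2 describes bladder-intact survival only as a proportion of the chemoradiation arm, so an arm difference there first needs a definition that covers both arms.
3. Label 171 per group as applying to the future trial, and state the one-sided level on which it rests.

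The change is to wording and reported statistics; recruitment, visits and treatment are untouched. The cost is that the trial gives up a non-inferiority claim it was very unlikely to be able to support.

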1. BACKGROUND AND SIGNIFICANCE

Radical cystectomy is the gold standard treatment for muscle-invasive bladder cancer. It involves removal of the bladder and prostate for men and anterior exenteration (including the bladder, uterus, ovaries, and part of the vagina) for women. Patients who were treated with the surgical approach report poor overall satisfaction, sexual function, urinary and bowel function, and health-related quality of life. The current NCCN (National Comprehensive Cancer Network) Clinical Practice Guidelines (version 2.2015) indicates bladder-preserving therapy with cystectomy reserved for tumor recurrence represents a safe and effective alternative to immediate radical cystectomy for muscle invasive bladder cancer.

According to the current NCCN guidelines, patients who are not surgical candidates (i.e. those with extensive comorbidities and/or poor performance status), chemoradiation can be used as a curative treatment regimen. This bladder-sparing therapy consist of (1) maximal transurethral resection of bladder tumor (TURBT), (2) induction external-beam radiation therapy with concurrent chemotherapy, (3) cystoscopic assessment of treatment response with prompt cystectomy for non-responders, and (4) active cystoscopic surveillance with salvage cystectomy at the first sign of invasive recurrence.

Retrospective studies have shown that the majority of chemoradiation patients achieves a clinical response and preserves the native bladder in >70% of patients while offering long-term survival rates comparable to contemporary cystectomy series.^{1,2}

We hypothesize that chemoradiation is non-inferior to radical cystectomy with regard to quality of life and progression free and bladder intact survival. Short of a randomized trial, any direct comparison of chemoradiation to radical cystectomy to address our hypothesis is difficult and must account for selection bias and confounding variables resulting from discordance between clinical, pathologic staging, functional status and comorbidities. Our proposed randomized pilot non-inferiority study aims to provide feasibility data for a larger randomized clinical non-inferiority trial comparing the efficacy and safety of chemoradiation and radical cystectomy.

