2. HYPOTHESIS AND SPECIFIC AIMS

Multiple prospective radiation therapy protocols have evaluated bladder-preserving chemoradiation therapy approach for muscle-invasive bladder cancer (MIBC), with radical cystectomy reserved for radiation failure. Aims of bladder preservation in MIBC are to offer a quality-of-life advantage and avoid potential morbidity or mortality of RC without compromising oncologic outcomes. Because of lack of level-1 evidence, oncologic equivalence of bladder preservation modality treatments compared with RC remains unknown.

2.1 HYPOTHESIS:

We hypothesized that chemoradiation is non-inferior to radical cystectomy for treatment of MIBC.

2.2 SPECIFIC AIMS:

SPECIFIC AIM 1a To determine and quantify quality of life in patients treated with radical cystectomy and chemo radiation therapy

1b To determine and quantify progression free survival and bladder-intact survival in patients treated with radical cystectomy and chemoradiation therapy,

SPECIFIC AIM 2a To evaluate genetic markers predicting response to chemoradiation by performing tissue RNA microarrays.

2b To assess the feasibility of conducting an adequately powered non-inferiority trial of the same design via recruitment rate, patient adherence to both treatment arm, and attrition.

2.3 STUDY DESIGN:

Our study will be a pilot, prospective, single-center, randomized non-inferiority trial comparing chemoradiation therapy to radical cystectomy. Patients diagnosed with muscle invasive bladder cancer after transurethral resection of bladder tumor and are surgical candidates will be randomized to either radical cystectomy (with neoadjuvant chemotherapy if suitable candidate) or chemoradiation.

Both treatment methods are considered “standard of care” recommended by the NCCN Clinical Practice Guidelines (http://www.nccn.org/professionals/physician_gls/pdf/bladder.pdf) in treating muscle invasive bladder cancer.

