4.3. Required Evaluations/Management (baseline prior to initiation of any protocol treatment)

- a) Cystoscopic evaluation by the participating urologic surgeon no more than 6 weeks prior to registration will include bimanual examination under anesthesia, as thorough as possible, a transurethral resection of the bladder tumor. Patients referred from an outside hospital with a muscularis propria-invading bladder tumor will be re-resected by the participating urologist.
- b) Radiologic evaluation including chest CT, abdominal and pelvic CT and bone scan no more than 6 weeks prior to start of treatment.
- c) Comprehensive metabolic panel (CMP) obtained no more than 4-6 weeks prior to registration

5. Randomization

5.1 Radical Cystectomy Arm- Those randomized to “Radical Cystectomy” will be scheduled for surgery. In brief, radical cystectomy is the removal of the entire bladder, nearby lymph nodes (lymphadenectomy), part of the urethra, and nearby organs that may contain cancer cells. In men the prostate, the seminal vesicles, and part of the vas deferens are also removed. In women the cervix, the uterus, the ovaries, the fallopian tubes, and part of the vagina are also removed. Participants in this group may also undergo neoadjuvant chemotherapy prior to the surgery as is the current standard of care. The decision for specific chemotherapy regimen is based on medical oncologist’s evaluation. All AE occurring during the study period will be assessed and attribution assigned.

The surgical approach, robotic versus open, is determined by patient and surgeon mutual preference. All urinary diversions will be done via an open incision and the mode of diversion, whether intracorporeal or extracorporeal (orthotopic neobladder, continent cutaneous diversion or ileal conduit) will be selected by mutual agreement of the surgeon and patient, as is customarily done. The extent of the lymph node dissection will be determined by the surgeon but at minimum will include the external iliac, obturator, and hypogastric regions.

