9. DATA COLLECTION & STUDY EVALUATIONS

Medical records will be reviewed prior to “Baseline Study Visit” to confirm study eligibility. After obtaining consent, socio-demographic data will be collected through chart review and interviews. Clinical data that will be collected include but not limited to bladder cancer treatment history, tumor characteristics, stage, laboratory results, medications and co-morbidity.

Study team member or clinic staff will measure height, weight, and vital signs at each specific study time point. Research blood will be drawn at each study time point. Blood and tissue samples may be banked under the optional study (HSC20050234H GU Tissue Bank). For those participants who declined to participate in the optional study, any leftover samples will be permanently de-identified through the GU Tissue Bank (HSC20050234H) honest broker system. At the close of this study, all biological materials collected will be rolled into HSC20050234 GU Tissue Bank.

9.1 Feasibility: We will report recruitment, visit dates, adherence, attrition rates and compliance with randomization for each arm of the study

9.2 Bladder-intact survival: We will report proportion of patients who failed chemoradiation and required salvage cystectomy

9.3 Quality of life: A self-assessment questionnaire using the European Organization for Research and Treatment of Cancer (EORTC) QLQ- C30 and FACT-Bladder will be used for QOL assessment at baseline, 3, 6, 9 and 12 months.⁸

9.4 Progression free survival: This will be measured from the date of finishing chemoradiation or radical cystectomy to the date of first documentation of progression. Progression will be determined using RECIST 1.1 criteria by the treating physician based on radiographic or pathologic evidence of disease progression, or death from disease. Any documented recurrence will be considered progression.⁹ The date of progression will be recorded.

9.5 Candidate gene expression analysis: For the participants who have consented to be part of the optional study (“GU Tissue Bank HSC20050234H), a microarray analysis will be performed on all bladder tumor specimens using Agilent Technologies (Agilent SurePrint G3 Human Gene Expression 8x60K v2) Microarray. Goal is to study the landscape of 50 important candidate genes, which are involved in bladder cancer (for example-BRAF, KRAS, EGFR, FGFR).

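### Bladder-intact survival is tested for non-inferiority against an arm whose assigned treatment removes the bladder, so the between-arm test is not a valid comparison

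*Combined protocol and SAP*

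**What the plan says.** Section 1 hypothesises that "chemoradiation is non-inferior to radical cystectomy with regard to quality of life and progression free and bladder intact survival". Aim 1b in Section 2.2 carries the endpoint into both arms: "To determine and quantify progression free survival and bladder-intact survival in patients treated with radical cystectomy and chemoradiation therapy". Section 11 turns this into a formal test: "we will test the hypothesis that chemoradiation is non-inferior to radical cystectomy with regard progression free survival and bladder intact survival". It summarises progression-free and bladder-intact survival by arm with Kaplan-Meier curves, and "non-inferiority will be assessed with a logrank test". Fisher's exact test is the fallback if the logrank fails.

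Section 5.1 describes the comparator: "radical cystectomy is the removal of the entire bladder", together with nearby nodes and organs.

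The only operational text for the endpoint is Section 9.2: "We will report proportion of patients who failed chemoradiation and required salvage cystectomy". This is a proportion in one arm. The documents give no event rule for the cystectomy arm and no non-inferiority margin for this endpoint. Nor do they give it a time origin; Section 9.4 states one (end of chemoradiation, or cystectomy) for progression-free survival only.

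**The concern.** A non-inferiority test asks whether the new treatment does acceptably well on an outcome that either arm could have had, well or badly. Retaining the bladder is not such an outcome when one arm is assigned to have it removed. The cystectomy arm's result then follows from how the event is defined, and the missing definition decides which arm is favoured.

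At stake is one of the three outcomes put to a non-inferiority test (quality of life, progression-free survival, bladder-intact survival). The trial could report chemoradiation as non-inferior, or as worse, on bladder-intact survival when the contrast mostly reflects what the comparator treatment is.

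**Working it through.** **Inputs.** 15 patients per arm (Sections 3.3 and 11); follow-up to 36 months (Section 7.1); bladder preservation above 70% with chemoradiation (Section 1). My assumptions are a two-sided 5% level, exponential event times on chemoradiation, and, where stated, surgery uniform over months 1 to 5 from a common origin.

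**The plan's own figure.** None is given for this endpoint. The 171 per group in Section 11 belongs to Aim 1a. It reproduces with one-sided alpha 2.5% and a margin of 5 points below control: (1.960 + 0.842)² × (0.6×0.4 + 0.5×0.5) / (0.10 + 0.05)² = 170.9, so 171. It has no bearing on this point.

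**Reading A: event is loss of the native bladder or death.**

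*Surgery at the time origin* (the Section 9.4 clock borrowed). All 15 cystectomy patients have the event at time 0, and no chemoradiation patient does.
- Observed minus expected in the cystectomy arm: 15 − 15×(15/30) = 7.5.
- Variance: 15 × (15/30) × (15/30) × (30−15)/(30−1) = 1.94.
- Chi-square: 7.5²/1.94 = 29.0, p about 7×10⁻⁸.

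The cystectomy risk set is then empty, so later chemoradiation events add nothing. The statistic is the same whether 0 or 15 of those patients go on to lose the bladder.

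*Surgery over months 1 to 5, simulated logrank:*

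| Chemoradiation 3-year bladder-intact survival | Trials favouring chemoradiation, all 15 operated on |
|---|---|
| 70%, 50%, 30% | about 100% |
| 10% | 99% |
| 2% | 89% |

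With all 15 operated on, chemoradiation was not significantly worse in any run.

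*Sensitivity to surgery not done.* At 30% bladder-intact survival on chemoradiation, the share favouring chemoradiation falls to about 85% if 2 of 15 cystectomy-arm patients are never operated on and stay event-free. It falls to about 44% if 3 are.

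*Fisher fallback against 15/15.* p = 0.042, still favouring chemoradiation, when 10 of 15 chemoradiation patients have had the event. It is 0.0996 at 11 of 15.

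**Reading B: event is salvage cystectomy after failed chemoradiation (Section 9.2).**

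A patient treated by primary cystectomy cannot have this event, so the comparator is 0/15.
- Fisher p is 0.0996 at 4/15 and 0.042 at 5/15, so the test turns against chemoradiation from 5 salvages on.
- At a 30% salvage rate, close to the complement of the Section 1 preservation figure, P(5 or more of 15) = 48%.
- The simulated logrank is non-significant in about 95%, 64%, 32% and 8% of trials at salvage rates of 10%, 20%, 30% and 40%.

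**Side by side.** Take 5 of 15 chemoradiation patients losing the bladder through salvage cystectomy, with no deaths and all 15 comparator patients operated on. Reading A gives Fisher p = 0.0002 in favour of chemoradiation. Reading B gives p = 0.042 against it.

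**The case against.** The strongest reply has four parts.

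1. *The result is not always predetermined.* A reader might infer that the outcome is fixed by design and tells us nothing about chemoradiation. The documents do not support that. Under Section 9.2, the only written definition, the result moves with the salvage count and so does reflect how chemoradiation performs. Under Reading A it is exactly fixed only when surgery sits at the time origin. It weakens materially if patients go without surgery, and adherence is itself something this pilot measures (Aim 2b). This part stands and limits the claim.

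2. *A third reading is open:* salvage cystectomy or death, with the planned cystectomy not counted. Both arms could then have events. That is true, but bladder loss would still count in one arm only, so the comparison would not be like for like.

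3. *The plan half-handles this already.* Section 9.2 reports a chemoradiation-arm proportion, and the Section 9.8 table lists bladder-intact survival under study processes, apart from the outcomes of interest. This shows that the remedy fits the plan. It does not withdraw the test in Section 11 or the hypothesis in Section 1.

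4. *It is a pilot.* Section 1 says it is meant to provide feasibility data, and nothing says that a bladder-intact claim would feed the larger trial. The consequence is therefore confined to what this trial would report. Section 11 still commits to the test.

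**Conclusion.** The concern holds as a point about the between-arm test. Under both readings the cystectomy arm gives no comparable bladder-retention data, and the reading decides the direction: chemoradiation is strongly favoured if bladder loss or death is the event, and can only tie or lose if salvage cystectomy is.

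The 29.0 requires surgery at the time origin and no chemoradiation event there. The simulated percentages rest on surgery in months 1 to 5, exponential event times and, except in the sensitivity runs, surgery in all 15. The Reading B Fisher results need only 0/15 in the comparator.

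The conclusion does not extend to the endpoint within the chemoradiation arm, which remains informative, or to the progression-free survival comparison. The missing margin is a separate gap; supplying one would not make this comparison valid.

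**What to change.** - **Sections 1 and 11:** remove bladder-intact survival from the between-arm non-inferiority hypothesis and test.
- **Aim 1b (Section 2.2):** amend to match, so that bladder-intact survival is quantified in the chemoradiation arm only. Confine the arm comparison to endpoints that can occur in both arms, such as progression-free survival.
- **Section 9.2:** state the time origin and whether death counts as an event. Report a Kaplan-Meier estimate from randomisation with its 36-month 95% confidence interval. Use an exact binomial interval only if 36-month status is known for every patient; for illustration, 11/15 = 73%, interval 45% to 92%.

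The cost is a wording amendment to these sections, with no new patients or data. The downside is the loss of one comparative claim.
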